3.8.5. Electrocardiograms

Descriptive statistics for ECG parameters (heart rate, PR interval, QRS interval, QT interval, and QTc interval) at baseline and change from baseline values at each assessment time point will be presented as overall for the open-label periods and by treatment group for the double-blind period. QTc interval will be calculated using both Bazett ($QTcB = QT/(RR)^{1/2}$) and Fridericia ($QTcF = QT/(RR)^{1/3}$) corrections; if RR is not available, it will be replaced with 60/HR in the correction formula.

Electrocardiogram parameter values are considered PCS if they meet or exceed the higher-limit PCS criteria listed in Table 6. The number and percentage of subjects with PCS post baseline ECG values will be tabulated by treatment group for the double-blind treatment period. The percentages will be calculated relative to the number of subjects with available non-PCS baseline values and at least 1 post baseline assessment for the double-blind treatment period. The numerator is the total number of subjects with available non-PCS baseline values and at least 1 PCS post baseline value for the double-blind treatment period. A supportive tabular display of subjects with PCS post baseline values will be provided, including the subject ID number, study center number, baseline, all post baseline (including non-PCS) values, and change from baseline.

Table 6: Criteria for Potentially Clinically Significant (PCS) QTcB and QTcF

Parameter	Criteria
QTcB and QTcF	>450 to ≤480 msec
	and change from baseline ≤30 msec
	and change from baseline >30 to ≤60 msec
	and change from baseline >60 msec
	>480 to ≤500 msec
	and change from baseline ≤30 msec
	and change from baseline >30 to ≤60 msec
	and change from baseline >60 msec
	>500 msec
	and change from baseline ≤30 msec
	and change from baseline >30 to ≤60 msec
	and change from baseline >60 msec
	Change from baseline >30 to ≤60 msec
	Change from baseline >60 msec

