10. Has clinically significant hypotension or hypertension not stabilized by medical therapy; a clinically significant cardiac arrhythmia, cardiomyopathy, or cardiac conduction defect; or has a clinically significant ECG abnormality at screening or Visit 2, including (but not limited to) the following:
 - For men, QT interval (corrected using the Fridericia formula; QTcF) >450 milliseconds

- For women, QTcF >470 milliseconds
11. Has a history of a myocardial infarction or unstable angina, including a silent myocardial infarction discovered on ECG
12. Has a positive drug screen at screening for opiates (including buprenorphine, norbuprenorphine, codeine, hydrocodone, hydromorphone, methadone, morphine, oxycodone, and oxymorphone) or meets criteria for any of the following medication restrictions:
- Has taken opioid agonists (eg, codeine, oxycodone, tramadol, or morphine) within 14 days prior to screening or anticipates needing to take opioid medication during the study period (eg, planned surgery)
 - Has taken opioid antagonists within 60 days before screening
 - Has received a long-acting formulation of any antipsychotic medication by intramuscular injection within 2 months prior to screening
 - Long-acting formulations of antipsychotics are also prohibited medications; therefore, administration should not occur or be planned to occur during screening (see [Section 8.4.2](#))
 - Has received clozapine for more than 1 week during the past year
 - Has used naltrexone (including ReVia[®]/Depade[®] and Vivitrol[®]) within 2 months prior to screening; naloxone, acamprosate (Campral[®]), disulfiram (Antabuse[®]), or other medication for alcohol dependence within 14 days prior to screening; or has been admitted to an alcohol detoxification program within the past 3 months (including current treatment at screening)
 - Is currently taking an antidepressant unless the subject has been on a stable dose for at least 30 days prior to screening and it is anticipated that the dose will not change during the subject's participation in the study. The medical monitor should be contacted with any questions about the appropriateness of including a subject taking an antidepressant medication. Antipsychotic use for depression is exclusionary.
 - Is currently receiving treatment with a hypoglycemic agent (eg, metformin, insulin, sulfonylurea, etc)

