8.3.22. Hematology, Biochemistry, and Urinalysis

Blood and urine samples for laboratory assessments will be collected at the time points specified in [Table 1](#), [Table 2](#), and [Table 3](#). Specific hematology, biochemistry, and urinalysis assessments are listed in [Table 4](#). Samples will be collected in accordance with the site’s usual procedures

and analyzed by a central laboratory. Follow-up samples may be obtained for repeat testing as clinically indicated.

An absolute neutrophil count $\leq 1.0 \times 10^3$ per μL anytime while on olanzapine should be cause for discontinuing a subject. A second test can be performed within 24 hours of availability of the laboratory result to confirm the finding if the investigator feels the result may be in error. Otherwise, the subject should be discontinued.

For all timepoints (except screening) where samples will be collected, fasting assessments (fasting for at least 10 hours prior to collecting samples) should be attempted as per standard of care [[Lilly USA 2013](#)]. However, fasting may present challenges, including an increased frequency of missed visits and re-scheduling, that could negatively impact the subject's treatment. Therefore, failure to fast should not be considered a protocol deviation.

Whether or not a subject fasts and the number of hours since the subject's last meal will be entered onto the appropriate eCRF.

TSH will only be measured at screening.

Table 4: Clinical Laboratory Assessments

Hematology	Biochemistry	Urinalysis

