14.5. Safety Analyses

Safety will be evaluated based on the incidence of TEAEs, laboratory test results, vital signs, ECG findings, C-SSRS results, abnormal movement rating scales results, as well as concomitant medications. Reported AE terms will be coded using the MedDRA (Medical Dictionary for Regulatory Activities) preferred terms and system organ classes.

The incidence of TEAEs will be summarized for each study period, treatment group, and overall by severity and by relationship to study drug. The summary tables will include the number and percent of subjects with TEAEs overall, by system organ class, and by preferred terms within each system organ class. Additional AE summary tables will be defined in the SAP.

Laboratory tests will be summarized by visit for the absolute value itself and for change from baseline by study period. Tables showing the shift from baseline will also be presented.

Potentially clinically significant (PCS) values for each relevant parameter will be defined in the SAP.

QT, QTcB, and QTcF intervals will be calculated at each ECG assessment. Interval data will be summarized by study period and treatment group at each time point for the absolute value and for changes from baseline. In addition, the number and percentages of subjects with post-baseline results QTcB and QTcF values >450, 480, or 500 milliseconds and an increase from baseline of >30 or 60 milliseconds from baseline will be summarized. Other ECG variables that are collected will be summarized as well.

C-SSRS will be summarized by number and percent of subjects with any abnormal findings at post-baseline visits by study period and treatment group. AIMS, BARS, and SAS will be summarized by study period and treatment group for the absolute value and for changes from baseline at each visit.

Concomitant medications will be coded using World Health Organization Drug Dictionary Anatomical Therapeutic Chemical (WHO-ATC) class. The number and percentage of subjects using concomitant medications will be summarized by study period and treatment group.

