3.8.3. Clinical Laboratory Parameters

Laboratory parameters will be presented in conventional units. Only scheduled laboratory parameters will be included in the summaries. All laboratory data, including those collected at unscheduled visits, will be included in the listings.

Laboratory results (baseline and change from baseline) for chemistry and hematology parameters will be summarized as overall for open-label periods and by treatment group for the double-blind period.

Clinical laboratory test values, scheduled or unscheduled, will be considered potentially clinically significant (PCS) if they meet PCS criteria listed in Table 2. The number and percentage of subjects who have PCS post baseline clinical laboratory values will be tabulated by treatment group for the double-blind period. The percentages will be calculated relative to the number of subjects with available non-PCS baseline values and at least 1 post baseline assessment for the double-blind treatment period. The numerator will be the total number of subjects with available non-PCS baseline values and at least 1 PCS post baseline value for the double-blind treatment period. A supportive tabular display of subjects with PCS post baseline values will be provided, including the subject ID number, study center number, baseline, and all post baseline (including non-PCS) values.

Table 2: Criteria of Potentially Clinically Significant (PCS) Abnormality for Selected Analytes

Parameters	Criteria
Albumin	<2.5 g/dL
Alkaline phosphatase (U/L)	$\geq 3 \times \text{ULN}$
Alanine aminotransferase (U/L)	$\geq 3 \times \text{ULN}$
Aspartate aminotransferase (U/L)	$\geq 3 \times \text{ULN}$
Bilirubin, total	$\geq 2.0 \text{ mg/dL}$
Blood urea nitrogen	$> 30 \text{ mg/dL}$
Cholesterol, random	$> 300 \text{ mg/dL}$
Cholesterol, fasting	$\geq 240 \text{ mg/dL}$
Cholesterol, HDL fasting	$\leq 30 \text{ mg/dL}$
Cholesterol, LDL fasting	$\geq 160 \text{ mg/dL}$
Creatine kinase (U/L)	$\geq 3 \times \text{ULN}$
Creatinine	$\geq 2.0 \text{ mg/dL}$
Glucose, random	$< 50 \text{ mg/dL}$ or $\geq 200 \text{ mg/dL}$
Glucose, fasting	$\geq 126 \text{ mg/dL}$
Potassium	$< 3 \text{ mmol/L}$ or $> 5.5 \text{ mmol/L}$
Lactate dehydrogenase (U/L)	$> 3 \times \text{ULN}$
Phosphate	$< 2 \text{ mg/dl}$ or $> 5 \text{ mg/dl}$
Prolactin (female)	$> 30 \text{ ng/mL}$
Prolactin (male)	$> 20 \text{ ng/mL}$
Sodium	$< 130 \text{ mmol/L}$ or $> 150 \text{ mmol/L}$

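### The QTc alert table does not say whether a non-PCS baseline is judged per row; read literally, it leaves out anyone above 450 ms at Visit 8

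*SAP*

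**What the plan says.** SAP 3.8.5 defines the flag first: "Electrocardiogram parameter values are considered PCS if they meet or exceed the higher-limit PCS criteria listed in Table 6". It then sets the denominator ("The percentages will be calculated relative to the number of subjects with available non-PCS baseline values and at least 1 post baseline assessment") and the numerator ("The numerator is the total number of subjects with available non-PCS baseline values and at least 1 PCS post baseline value"), both for the double-blind period.

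Table 6 covers QTcB and QTcF with the same limits for men and women. Its lowest band is ">450 to ≤480 msec". The next runs from above 480 to 500 ms, and the last is above 500 ms. Each band is split by change from baseline (at most 30, above 30 to 60, above 60 ms). Two further rows use change alone.

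SAP 3.1 takes the double-blind baseline from the last value on or before the first double-blind dose, at Visit 8. Protocol 7.2, criterion 10, applies its ECG limits at screening or Visit 2. Men are excluded above a QTcF of 450 ms; the limit for women reads "For women, QTcF >470 milliseconds". No numeric QTcB limit is given, and Protocol 7.3 has no QTc criterion for randomization.

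Protocol 14.5 plans to count subjects whose post-baseline results are "QTcB and QTcF values >450, 480, or 500 milliseconds", and increases above 30 or 60 ms. It puts no condition on the baseline value. SAP Section 5, which records changes from the protocol, mentions only endpoints. SAP 3.8.3 uses the same restriction for laboratory values: "The numerator will be the total number of subjects with available non-PCS baseline values and at least 1 PCS post baseline value".

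**The concern.** Requiring a normal baseline makes sense when a table has one limit, because it then counts new abnormalities. Table 6 is graded. A subject already in its lowest band at baseline can still have a new and more serious event by crossing 480 or 500 ms, and needs a smaller rise to do so than a subject starting lower.

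Read literally, one filter for the whole table removes such subjects from every row, including the change rows, where the baseline level is not the question. The rows above 480 ms, above 500 ms and for large rises are the ones a safety reader looks at first. Their by-arm percentages could omit cases that occurred. Visit 8 also follows four weeks of olanzapine and two weeks of olanzapine plus samidorphan, so a baseline above 450 ms may itself have arisen on treatment.

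**Working it through.** The plan states no figure that depends on this rule, so there is nothing to reproduce. The check applies the rule to individual cases.

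**1. Can a Visit 8 value exceed 450 ms?** Yes. A woman with QTcF of 451 to 470 ms passes the entry limit, QTcB has no numeric limit, and no QTc criterion applies at randomization. A man who rises above 450 ms after Visit 2 is in the same position.

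**2. What is counted?** Literal means that the baseline must be below every Table 6 limit. Closed band means that the baseline must lie outside the band being counted. Cumulative is the rule proposed below (threshold rows only).

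| Visit 8 (ms) | Later (ms) | Change (ms) | Literal | Closed band | Cumulative |
|---|---|---|---|---|---|
| 451 | 485 | 34 | not counted | >480 to ≤500 | >480 |
| 451 | 505 | 54 | not counted | >500 | >480, >500 |
| 460 | 485 | 25 | not counted | >480 to ≤500 | >480 |
| 460 | 505 | 45 | not counted | >500 | >480, >500 |
| 470 | 485 | 15 | not counted | >480 to ≤500 | >480 |
| 470 | 505 | 35 | not counted | >500 | >480, >500 |
| 485 | 505 | 20 | not counted | >500 | >500 |
| 510 | 490 | −20 | not counted | >480 to ≤500, as a new case | none |

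Of the first six cases, the literal reading counts none, in numerator or denominator. The unrestricted Protocol 14.5 count includes all six. Four of the six also rise by more than 30 ms (34, 54, 45 and 35) and are lost from the change rows as well. None of the six exceeds 60 ms; from 460 ms that would need a value above 520 ms, and such a subject would be lost in the same way.

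**3. Empty rows.** Under the literal reading the baseline is at most 450 ms. A later value above 480 ms then implies a change above 480 − 450 = 30 ms, and a value above 500 ms implies a change above 50 ms. The rows for a change of at most 30 ms in the two upper bands can never hold a subject. The 460 to 485 and 485 to 505 cases are the kind those rows exist to show.

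**4. Closed bands.** A baseline of 510 ms is not inside the band from above 480 to 500 ms, so it is non-PCS for that row. Improvement to 490 ms then enters the numerator as a new case.

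**5. Size, on assumptions only.** Take 135 per arm, with 3 to 14 subjects in one arm above 450 ms at Visit 8 and none above 500 ms. Suppose 2 of these later exceed 500 ms, and 1 subject among the rest does.

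- Literal: 1/(135 − 3) = 1/132 = 0.76%, to 1/(135 − 14) = 1/121 = 0.83%.
- Unrestricted, or with baseline ≤500 ms: 3/135 = 2.22%.

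The share above 450 ms at Visit 8 is not in the documents. With an assumed QTcB mean of 425 to 440 ms and SD of 20 to 22 ms, the normal tail above 450 ms is about 11% to 32%, or 29 to 88 of 270. With an assumed 25% to 50% women, QTcF mean 410 to 425 ms and SD 18 to 20 ms, about 1 to 13 women would lie between 451 and 470 ms.

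**The case against.** The strongest reply is that Table 6 itself shows a row-by-row intent, since two rows would otherwise be empty. That is plausible, and it is why the literal reading cannot be called the plan's settled meaning. One could add that the words meet or exceed in the flag definition make a baseline of 510 ms PCS for the middle band as well, which would cure the closed-band problem. But Table 6 prints upper limits on its bands, and the SAP says neither thing. If row-by-row was meant, the fix only writes it down.

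Second, Protocol 14.5 names no denominator and Protocol 14.2 leaves detail to the SAP, so counting new onsets may be a deliberate choice. This stands for the denominator. Removing subjects from the numerator changes what is counted, and SAP 3.8.4 uses no such filter for weight or vital signs.

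Third, the affected subjects do not vanish. SAP 3.8.5 also plans unfiltered change-from-baseline statistics by arm and a by-subject display of post-baseline PCS values, with no baseline restriction stated. That is correct, but neither corrects the percentages, and treatment group is not among the contents named for the display.

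Fourth, expected numbers may be small. With an assumed SD of change of 15 ms and no drug effect, the chance that one reading exceeds 500 ms from 465 ms is P(Z > 35/15), about 1%. For 1 to 13 women that is 0.01 to 0.13 expected subjects per reading. This argues against alarm, but such rows exist for rare events.

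A reader might also infer that the laboratory rule hides the neutrophil stopping event. The documents do not support that. Protocol 8.3.22 says a count at or below 1.0 × 10³/µL "anytime while on olanzapine should be cause for discontinuing a subject", and Protocol 7.4 places this under discontinuation for adverse events. SAP 3.8.1 tabulates adverse events leading to discontinuation by arm, and SAP 3.3 tabulates discontinuation reasons; neither filters on baseline. The laboratory filter also acts per analyte, and shift tables for metabolic parameters cover part of what it removes.

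**Conclusion.** The point holds as a defect in the stated rule. SAP 3.8.5 is silent on how a non-PCS baseline is judged, and neither the literal nor the closed-band reading gives a sound table. The literal one drops every subject above 450 ms at Visit 8 from that parameter's PCS percentages; the closed-band one can count an improvement as a new case. It should be settled before unblinding.

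Two stronger inferences fail. One is that the subjects lost are the women admitted at 451 to 470 ms. The entry limit applies at screening or Visit 2, whereas the filter uses Visit 8, so such a woman is dropped only if still above 450 ms then. Men above 450 ms at Visit 8, and anyone with QTcB above 450 ms, are treated alike. The other is that the rule biases the comparison between arms. The baseline precedes double-blind dosing, so the filter acts the same way on both arms. What can be lost is events and the true frequency in each arm.

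The size is unknown. The counts and distributions used above are assumptions, and the documents give no Visit 8 QTc data. The laboratory part is secondary.

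**What to change.** In SAP 3.8.5, replace the single filter with cumulative thresholds, each with its own baseline condition and at least one post-baseline ECG:

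- above 450 ms: baseline ≤450 ms;
- above 480 ms: baseline ≤480 ms;
- above 500 ms: baseline ≤500 ms;
- change rows: all subjects with a baseline and a post-baseline ECG.

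Alternatively, keep the filtered table and report the unrestricted Protocol 14.5 counts by arm beside it. Record any remaining departure from Protocol 14.5 in SAP Section 5.

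For laboratory values, a reporting row for neutrophils at or below 1.0 × 10³/µL, with its own baseline condition, is optional.

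The cost is SAP wording and a small programming change on data already collected. The only downside is that denominators differ by row, so each row must print its own.

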3.8.6. Abnormal Movement Scales

Extra pyramidal symptoms (EPS) will be evaluated as AEs and also as assessed by abnormal movement scales. Abnormal movement scales will include the following: Abnormal Involuntary Movement Scale (AIMS), Barnes Akathisia Rating Scale (BARS), and Simpson-Angus Scale (SAS).

For all abnormal movement scales, total scores and subscale scores will be summarized by treatment group at each visit for the absolute value and for changes from baseline.

Number and percentage of subjects meeting the criteria for treatment emergent Parkinsonism (SAS total score >3), for treatment emergent akathisia (BARS global clinical assessment of akathisia score ≥2), for treatment emergent dyskinesia (AIMS score ≥3 on any of the first 7 items, or a score ≥2 on two or more of any of the first 7 items) at any post-baseline visit will be summarized by treatment group.

A listing will be provided for every abnormal movement scale. Listing for treatment emergent EPS will be provided.

3.8.7. Columbia Suicide Severity Rating Scale (C-SSRS)

The C-SSRS is a questionnaire used to measure the presence and intensity of suicidal ideation and behavior.

Suicidal behavior and suicidal ideation will be summarized descriptively. The number of subjects with suicidal ideation and suicidal behavior at lifetime history, open-label periods and double-blind treatment period and safety follow-up period will be summarized by overall or by treatment group when applicable.

Supportive tabular display of subjects with all values will be provided, including subject ID number, treatment group, visit number, intensity of suicidal ideation, suicidal behavior type, and lethality of suicidal behavior.

Table 7: C-SSRS Categories for Analysis

Category	C-SSRS Item response is "YES"
Suicidal behavior	
 • Preparatory acts or behavior • Aborted attempt • Interrupted attempt • Actual attempt • Complete suicide
Suicidal ideation	
 • Wish to be dead • Non-specific active suicidal thoughts • Active suicidal ideation with any methods (not plan) without intent to act • Active suicidal ideation with some intent to act, without specific plan • Active suicidal ideation with specific plan and intent

3.9. Pharmacokinetic/Pharmacodynamic Data Analysis

Subject listings for PK sampling time, prior drug dosing time, and plasma concentrations of olanzapine, samidorphan, and RDC-9986 (metabolite of samidorphan) will be provided. Plasma concentration data obtained from this study may be included in a subsequent population PK analysis or other post-hoc analyses.

4. INTERIM ANALYSES

Not applicable.

5. CHANGES IN CONDUCT OR PLANNED ANALYSES FROM THE PROTOCOL

Two endpoints, which have been included in the study protocol as the other endpoints, are elevated to the secondary endpoints in the SAP ([Section 3.7.3](#)).

Three exploratory endpoints, which have not been specified in the protocol, are included in the SAP ([Section 3.7.5](#)).

6. DEFINITIONS AND CONVENTIONS FOR HANDLING OF THE DATA

Dataset specifications will be provided in a separate document.

6.1. Analysis Visit Windows

Scheduled analysis visits are visits upon scheduled time points as specified in the protocol ([Table 1-3 Schedule of Visits and Assessments](#)).

Scheduled analysis visits during the study period will be the same as the nominal visits collected in eCRF. There will be one valid value of assessment kept for each scheduled analysis visit in summary/analysis statistics.

Unscheduled visits are visits with data not collected on the scheduled time point. Unscheduled visits will not be used for by-visit summary/analysis statistics unless specified otherwise.

All unscheduled visits will be included as collected in eCRF in listings.

The V38/ET visit can be mapped to a scheduled visit and be used for analysis and summaries only if there is no valid value already at the mapped visit.

A mapped V38/ET visit will be treated as a scheduled visit to be included in table summaries. Otherwise, it will be treated as an unscheduled visit.

Four rules will be used to map an ET visit.

- First, a 7-day (inclusive) window (\leq last dose date + 7) will be used to determine if the assessment at the ET visit is considered to be an on-treatment result. If an ET visit is within 7 days after the last dose of samidorphan/placebo, it will be considered as a valid on-treatment visit.
- Second, visit windows (inpatient stay is excluded) will be applied to determine to which visit a V38/ET valid on-treatment assessment can be mapped to. Visit windows are defined in Table 8 below.

Table 8: Visit Window Definition

Analysis Visit to be Mapped to	Target Study Day	Visit Day	Visit Window
Visit 2	Study day -28	Day -28	[-28, -25]
Visit 3	Study day -21	Day -21	[-24, -18]

Table 8: Visit Window Definition (Continued)

Analysis Visit to be Mapped to	Target Study Day	Visit Day	Visit Window
Visit 4	Study day -14	Day -14	[-17,-11]
Visit 5	Study day -7	Day -7	[-10, 0]
Visit 6	Study day 1	Day 1	1
Visit 7	Study day 8	Day 8	[2, 11]
Visit 8	Week 3	Day 15	[12, 21]
Visit 9	Week 5	Day 29	[22, 35]
Visit 10	Week 7	Day 43	[36, 57]
Visit 12	Week 11	Day 71	[58, 85]
Visit 14	Week 15	Day 99	[86, 113]
Visit 16	Week 19	Day 127	[114, 141]
Visit 18	Week 23	Day 155	[142, 169]
Visit 20	Week 27	Day 183	[170, 197]
Visit 22	Week 31	Day 211	[198, 225]
Visit 24	Week 35	Day 239	[226, 253]
Visit 26	Week 39	Day 267	[254, 281]
Visit 28	Week 43	Day 295	[282, 309]
Visit 30	Week 47	Day 323	[310, 337]
Visit 32	Week 51	Day 351	[338, 365]
Visit 34	Week 54	Day 379	[366, 393]
Visit 36	Week 59	Day 407	[394, 421]
Visit 38	Week 63	Day 435	[422, Day of Safety follow-up -1]

Visit Day is calculated as visit date – date of the first dose of ALKS 3831 (scheduled on Visit 6) + 1.

- Third, V38/ET visit can only be mapped to the same treatment period as the last scheduled visit. Otherwise, ET visit will be considered as unscheduled visit. Additionally, V38/ET visit can only be mapped to a scheduled visit that a particular assessment is taken based on the protocol.
- Four, for subjects who discontinued before visit 6, an on-treatment V38/ET results as defined above, will be mapped to the next scheduled visit, if within the same treatment period as the last scheduled visit.

Last post baseline values are defined as the last valid post baseline values collected for each subject during the treatment period or a specified reporting period.

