3.7.3.1.3. Additional Analysis on the Rate and Number of EEDS

Since the EEDS consists of a series of individual criteria, number and percent of subjects who met each individual criterion will be provided. The treatment groups will be compared by the logistic regression model adjusting for the baseline PANSS total score and drinking status.

In addition, the duration of IAC confirmed hospitalizations related to the underlying disease will be summarized by treatment group.

3.7.3.2. Proportion of Subjects with at least 1 Level Decrease in World Health Organization (WHO) Drinking Risk Level from Baseline to Week 24 of Double-blind Treatment (Study Week 27)

The alcohol consumption per day at each visit will be calculated based on the number of drinks per day as follows.

$$\text{Alcohol consumption per day} = \frac{\text{total number of drinks} \times 14 \text{ gram}}{\text{total number of days}}$$

The risk of the alcohol consumption will be categorized based on the alcohol consumption per day using the criteria in Table 1. Proportion of subjects with at least 1 level decrease in World Health Organization (WHO) drinking risk level³ from baseline to week 24 of double-blind treatment (study week 27) will be compared between two treatment groups using the logistic regression model based on LOCF (last observation carried forward) imputation for the missing data, that is, the last observed non-missing post-baseline value will be carried forward for the missing post baseline assessments. The model will include the treatment group as factor and adjust for the baseline PANSS total score and drinking status.

Table 1: Criteria for risk of alcohol consumption on a single drinking day

Risk Category	Males	Females
Abstinence	0 g	0 g
Low Risk	1 to 40 g	1 to 20 g
Medium Risk	41 to 60 g	21 to 40 g
High Risk	61 to 100 g	41 to 60 g
Very High Risk	≥ 101 g	≥ 61 g

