3.7.4. Other Efficacy Endpoints

Other efficacy endpoints for the double-blind treatment period are:

- The proportion of subjects with psychosocial events indicative of exacerbation of symptoms during the double-blind treatment period
- The rate and number of psychosocial events indicative of exacerbation of symptoms during the double-blind treatment period
- Change from baseline in PANSS total Score, Positive Score, Negative Score, and General Psychopathology Score during the double-blind treatment period
- Change from baseline in Clinical Global Impression–Severity (CGI-S) score during the double-blind treatment period
- Clinical Global Impression–Improvement (CGI-I) score during the double-blind treatment period
- Complete response profile of drinking during the double-blind treatment period
- Change from baseline in visual analogue score (VAS) for perception of desire for alcohol during the double-blind treatment period

3.7.4.1. Proportion of Subjects with Psychosocial Events Indicative of Exacerbation of Symptoms during the Double-blind Treatment period

The proportion of subjects with psychosocial events indicative of exacerbation of symptoms (defined in [study protocol section 11.2¹](#)) will be analyzed similarly as the primary analysis of the primary efficacy endpoint ([Section 3.7.2.1](#)). The incidence rate will be estimated by Kaplan-Meier estimate. The treatment comparison will be performed using the log-rank test and hazard ratio will be estimated by the Cox proportional hazards model.

3.7.4.2. Rate and Number of Psychosocial Events Indicative of Exacerbation of Symptoms during the Double-blind Treatment Period

The annualized rate and number of psychosocial events indicative of exacerbation of symptoms will be analyzed in the same way as the rate and number of EEDS ([Section 3.7.3.1](#)).

3.7.4.3. Change from Baseline in PANSS Total Score, Positive Score, Negative Score, and General Psychopathology Score during the Double-blind Treatment Period

Change from baseline of double-blind period in PANSS total score and subscale scores will be analyzed using ANCOVA (analysis of covariance) model with treatment group as factor and corresponding baseline value as the covariates for the ITT population. The ANCOVA model will be based on the LOCF imputation.

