7. GENERAL STATISTICAL METHODOLOGY

In general, summary statistics (n, mean, standard deviation [SD], median, minimum, and maximum for continuous variables, and number and percentage of subjects in each category for categorical variables) will be provided by treatment group. All summary tables will be based on observed data, and missing values will not be imputed unless otherwise indicated. Measurements collected from unscheduled visits or repeated assessments will not be included in the by-visit summary tables or figures, or the derivation of the last post-baseline value during treatment, but will be included in the analyses for the PCS post-baseline values, and subject listings. Source data for the summary tables and statistical analyses will be presented as subject data listings.

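### SAP 6.1 and Section 7 together keep an on-treatment early-termination score out of LOCF whenever it cannot be mapped to a scheduled visit

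*SAP*

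**What the plan says.** Protocol 7.4 asks subjects who leave early to attend an ET visit with the Visit 38 procedures. Protocol Table 3 accordingly shows PANSS, CGI-S, CGI-I, TLFB and VAS in the combined 38/ET column, so these data are collected.

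SAP 6.1 counts an ET visit as on treatment if it falls within 7 days of the last samidorphan or placebo dose. It then limits its use: "The V38/ET visit can be mapped to a scheduled visit and be used for analysis and summaries only if there is no valid value" already present at that visit. A further rule works measure by measure: "V38/ET visit can only be mapped to a scheduled visit that a particular assessment is taken based on the protocol". If mapping fails, "Otherwise, it will be treated as an unscheduled visit", and "Unscheduled visits will not be used for by-visit summary/analysis statistics unless specified otherwise".

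SAP Section 7 keeps unscheduled and repeated measurements out of by-visit tables and figures, "or the derivation of the last post-baseline value during treatment".

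Two other places are worded more broadly. The only explanation of LOCF, in SAP 3.7.3.2, is that "the last observed non-missing post-baseline value will be carried forward for the missing post baseline assessments". The closing sentence of SAP 6.1 reads: "Last post baseline values are defined as the last valid post baseline values collected for each subject during the treatment period" or a given reporting period.

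LOCF is used for the secondary WHO drinking-level endpoint (3.7.3.2), PANSS (3.7.4.3), CGI-S (3.7.4.4), CGI-I response (3.7.4.5), the by-visit categorical drinking endpoints (3.7.4.6.1) and VAS (3.7.4.7). The PANSS ANCOVA is specified with the "corresponding baseline value as the covariates for the ITT population"; the CGI-S ANCOVA is also stated for the ITT population.

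**The concern.** LOCF is meant to represent a leaver by the last score obtained on treatment. The ET visit is planned to capture that score at discontinuation. Under the mapping rule, whether it is used depends on where the ET day falls in the Table 8 windows. After an attended Visit 12 on Day 71, an ET on Day 85 is dropped and one on Day 86 is used, with nothing clinical to separate them.

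Two consequences follow. For most affected subjects, an older score replaces the one closest to discontinuation. For some very early leavers there is no post-baseline score at all, so they cannot enter ANCOVAs that are described as ITT analyses.

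**Working it through.** The SAP gives no figure for this, so the check is a count of days.

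**Inputs.** SAP Table 8 (days counted from the first ALKS 3831 dose):
- Visit 8: Day 15, window 12-21
- Visit 9: Day 29, window 22-35
- Visit 10: Day 43, window 36-57
- Visit 12: Day 71, window 58-85
- Then every 28 days to Visit 36 (Day 407), each window running from 13 days before to 14 days after target. Visit 38 is Day 435 and its window opens on Day 422.

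Protocol Tables 2 and 3: PANSS and TLFB are scheduled at Visits 8, 9, 10, 12 and every second visit to 38. CGI-S, CGI-I and VAS follow the same pattern without Visit 9.

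**Assumptions.** Earlier visits are attended on target, and ET is within 7 days of the last dose. An ET day is excluded if its window already holds a value or belongs to a visit where the measure is not scheduled.

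| After visit(s) | PANSS: excluded / possible ET days | CGI-S, CGI-I, VAS: excluded / possible ET days |
|---|---|---|
| 8 | Days 16-21: 6 / 13 | Days 16-35: 20 / 27 |
| 9 | Days 30-35: 6 / 13 | not scheduled |
| 10 | Days 44-57: 14 / 27 | 14 / 27 |
| 12 to 24 (7 intervals) | 98 / 189 | 98 / 189 |
| Total to Day 266 | 124 / 242 (51%) | 132 / 243 (54%) |
| 26 to 36 (6 intervals) | 84 / 162 | 84 / 162 |
| Total to Day 434 | 208 / 404 (51%) | 216 / 405 (53%) |

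Per four-week interval from Visit 10 the share is 14/27 = 52%.

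**No value to carry.** In the Visit 8 row the only earlier value is baseline. That is 6 days for PANSS and 20 days for CGI-S, CGI-I and VAS.

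**Age of the carried value elsewhere, to Day 266.** Within a full interval the gaps are 1 to 14 days and sum to 105; after Visit 9 they are 1 to 6 and sum to 21.
- PANSS: (21 + 8 × 105) / 118 = 861/118 = 7.3 days on average.
- CGI-S, CGI-I, VAS: (8 × 105) / 112 = 840/112 = 7.5 days.

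**Visits off target.** The ±2-day window is printed only in Protocol Table 1, so applying it to double-blind visits is an assumption. If all visits run 2 days late, 12 of 27 days (44%) are excluded per interval from Visit 12; if 2 days early, 16 of 27 (59%). The largest gap becomes 12 or 16 days. Days with no post-baseline value become 4 to 8 for PANSS and 18 to 22 for the other three scales.

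**Drinking endpoints.** TLFB follows the PANSS schedule. Before Visit 20 (Day 183), where the WHO endpoint is read, excluded ET days are 6 + 6 + 14 + 4 × 14 = 82 of 13 + 13 + 27 + 4 × 27 = 161 (51%). An unmapped ET TLFB covers only 1 to 14 days after an attended TLFB visit.

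**The case against.** A reader might infer that the SAP contradicts itself and leaves the matter open. The documents do not support that. 6.1 admits ET values to analysis only when mapped, and Section 7 expressly bars unscheduled measurements from the last post-baseline value. Those are the specific rules. The LOCF phrase in 3.7.3.2 explains the term and does not say which records are eligible. The reference in 6.1 to valid values fits exclusion too, because the same section keeps one valid value per scheduled visit. Exclusion is therefore the operative rule, and the broader wording is only loose.

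It can also be said that the substitute score is only about a week older on average in a 9- to 15-month period, and that the separate dataset and programming specifications, not available here, may already settle record selection.

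These arguments stand and keep the point small. They do not answer it. One value per visit is a sound rule for observed by-visit tables, but LOCF fills later, missing visits: an ET score on Day 80 would feed Visit 14 onward without displacing the observed Visit 12 score. Nor do they restore the early leavers with no post-baseline value to the ITT analyses.

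**Conclusion.** The point holds as a minor one about the effect of the rule, with a secondary wording gap because LOCF is not named in 6.1 or Section 7. Followed as written, the rule drops the on-treatment score nearest discontinuation on about half of possible ET days, given attended on-target visits and ET within 7 days of the last dose. It also leaves no post-baseline value after an ET on Days 16-21 (PANSS) or Days 16-35 (CGI-S, CGI-I, VAS). The four scales are all other efficacy endpoints; the secondary WHO drinking-level endpoint and the by-visit drinking endpoints fall under the same rule.

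Two stronger inferences are not supported. The first is that half of all leavers lose their last score: the counts are shares of days, and would equal shares of leavers only if ET days were spread evenly. The second is that the treatment comparison is biased in a known direction: neither the number of subjects nor the direction can be derived from the documents. The primary time-to-EEDS analysis does not use LOCF, and Section 7 keeps unscheduled values in the PCS analyses.

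**What to change.** State in SAP 6.1 and Section 7 that, for LOCF and for the last post-baseline value of PANSS, CGI-S, CGI-I and VAS, an ET assessment in the double-blind period that meets the existing 7-day rule is eligible even if it cannot be mapped. Say in the same place that all other unscheduled or repeated assessments stay excluded. This limit matters: a general last-on-treatment-value rule would also admit the ad hoc EEDS-confirmation visits of Protocol 8.5, where PANSS, CGI-S and CGI-I are repeated because a subject has met a worsening criterion. Observed by-visit summaries stay as they are.

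For the WHO drinking-level and by-visit drinking endpoints, state in 3.7.3.2 that LOCF uses scheduled or mapped TLFB visits only, and use the short ET TLFB interval in a sensitivity analysis. An ET on Days 16-21 would then still give no post-baseline TLFB value in the main analysis.

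The cost is a few sentences and minor programming before unblinding, with no new data. LOCF values will change for some early leavers, and the separate dataset specifications must match.
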